14.2.3 Adverse Events of Special Interest (AESI)

For this protocol only, specific adverse events, or groups of adverse events, will be followed as part of standard safety monitoring activities. These events (regardless of seriousness) will be reported to BMS per SAE reporting timelines.

14.2.3.1 *Major Hemorrhage*

Major hemorrhage is defined as any of the following:

- Any treatment-emergent hemorrhagic adverse events of Grade 3 or higher*. Any treatment-emergent serious adverse events of bleeding of any grade
- Any treatment-emergent central nervous system hemorrhage/hematoma of any grade

**All hemorrhagic events requiring transfusion of red blood cells should be reported as grade 3 or higher AE per CTCAE v4.03.*

Events meeting the definition of major hemorrhage will be captured as an event of special interest.

14.2.4 Additional AE Reporting Requirements

14.2.4.1 *Reporting to the FDA*

The study PI (or designee) will be responsible for contacting the Office of IND Development and Regulatory Affairs (OIDRA) at COH to ensure prompt reporting of safety reports to the FDA. OIDRA will assist the PI with the preparation of the report and submit the report to the FDA in accordance with the [City of Hope Clinical Research Adverse Event and Unanticipated Problem policy](#).

Serious Adverse Events meeting the requirements for expedited reporting to the Food and Drug Administration (FDA), as defined in [21 CFR 312.32](#), will be reported as an IND safety report using the [MedWatch Form FDA 3500A for Mandatory Reporting](#).

The criteria that require reporting using the Medwatch 3500A are:

- Any unexpected fatal or life threatening adverse experience associated with use of the drug must be reported to the FDA no later than 7 calendar days after initial receipt of the information [\[21 CFR 312.32\(c\)\(2\)\]](#)
- Any adverse experience associated with use of the drug that is both serious and unexpected must be submitted no later than 15 calendar days after initial receipt of the information [\[21 CFR 312.32\(c\)\(1\)\]](#)
- Any follow-up information to a study report shall be reported as soon as the relevant information becomes available. [\[21 CFR 312.32\(d\)\(3\)\]](#)

In addition, the Study PI will submit annually within 60 days (via COH OIDRA) of the anniversary date of when the IND went into effect, an annual report to the FDA which is to include a narrative summary and analysis of the information of all FDA reports within the reporting interval, a summary report of adverse drug experiences, and history of actions taken since the last report because of adverse drug experiences.

14.2.4.2 *Reporting to BMS*

Following the subject's written consent to participate in the study, all SAEs, whether related or not related to study drug, must be collected, including those thought to be associated with protocol-specified procedures. All SAEs must be collected that occur within 100 days of discontinuation of dosing.

All SAEs must be collected that occur during the screening period. If applicable, SAEs must be collected that relate to any protocol-specified procedure (eg, a follow-up skin biopsy). The investigator should report any SAE that occurs after these time periods that is believed to be related to study drug or protocol-specified procedure.

SAEs, whether related or not related to study drug, and pregnancies must be reported to BMS within 24 hours. SAEs must be recorded on BMS or an approved form; pregnancies on a Pregnancy Surveillance Form.

SAE Email Address: [contact]

SAE [contact]

If only limited information is initially available, follow-up reports are required. (Note: Follow-up SAE reports should include the same investigator term(s) initially reported.)

If an ongoing SAE changes in its intensity or relationship to study drug or if new information becomes available, a follow-up SAE report should be sent within 24 hours to the BMS (or designee) using the same procedure used for transmitting the initial SAE report.

All SAEs should be followed to resolution or stabilization.

The Sponsor/Investigator will ensure that all SAEs in the clinical database are reported to BMS and any applicable health authority during the conduct of the study including periodic reconciliation.

For studies conducted under an Investigator IND in the US, any event that is both serious and unexpected must be reported to the Food and Drug Administration (FDA) as soon as possible and no later than 7 days (for a death or life-threatening event) or 15 days (for all other SAEs) after the investigator's or institution's initial receipt of the information (see Section 14.2.4.1 above). BMS will be provided with a simultaneous copy of all adverse events filed with the FDA.

14.2.4.3 Reporting to Participating Investigators

The Study PI (or designee) will report all reportable serious adverse events to participating investigators as an IND Safety Report occurring within 30 calendar days of receipt of sponsor (lead site) notification, and indicate whether or not a protocol and/or consent form change is required. A cover letter will indicate the protocol title, the IND#, whether the FDA was informed, and, for non-COH sites, a statement that the report should be submitted to their local IRB for review as an IND safety report if applicable per local IRB policy.

The Study PI will also forward to participating sites all IND safety reports received from BMS, indicating whether a consent form or protocol change is required within 30 days of notification to Study PI.

15 Protocol Deviations and Single Subject Exceptions

Deviations from the protocol should be avoided, except when necessary to eliminate an immediate hazard(s) for the protection, safety, and well-being of a research participant. As a result of deviations, corrective actions are to be developed by the study staff and implemented promptly. All protocol deviations and planned protocol deviations will be reported in accordance with the [Clinical Research Protocol Deviation policy](#).

Non-COH Sites:

Deviations meeting the criteria specified in the Clinical Research Protocol Deviation policy (Appendix X) will be reported to the Data Coordinating Center (DCC) and PI within **24 hours** of notification that the event occurred.

Procedure for reporting deviations to the COH DCC:

1. Document the deviation on the Deviation Reporting Coversheet. This modifiable Microsoft Word document is available from the DCC. An electronic signature on this document will be accepted.
2. Scan and email the Deviation Reporting Coversheet to [contact] and [contact] **within 24 hours** of notification of the deviation with the email subject title of "COH IRB # Deviation". If an email receipt from the DCC is not received within one working day, please email [contact].
3. Sites are to report to their local IRB and DSMC per their site's specific institutional and IRB guidelines. As soon as possible, non-COH sites will provide to the COH DCC copies of the IRB and/or DSMC submission and corresponding response(s).

16 Study Oversight, Quality Assurance, and Data & Safety Monitoring

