5.1.5 Treatment Schedule

For a tabular view of the treatment, monitoring, and follow-up schedule, see study calendar in Section 10. Cycle length is 21 days for NIVO + ICE and 14 days for Nivolumab only.

| | | |
|--|-----------|-----|
| | Nivolumab | ICE |
|--|-----------|-----|

| | | |
|---|---|--|
| Nivolumab only | 240 mg IV every 2 weeks for 6 or 12 weeks. | N/A |
| NIVO + ICE stage, Dose Level 1 | 240 mg IV every 3 weeks (to synchronize with the ICE schedule) for 6 weeks on D1 | Ifosfamide 5000 mg/m ² IV on Day 2 Carboplatin AUC 5 IV on Day 2 Etoposide 100 mg/m ² IV on Days 1-3 |
| NIVO + ICE stage DoseLevel -1 (De-escalation) | 240 mg IV at 3 weeks and 6 weeks on Day 1 | ICE to begin on Day 8 instead of Day 1 |
| Cohort B – 1 dose Nivolumab, then NIVO + ICE | 240 mg IV at week 1, then week 3 (Cycle 2), week 6 (Cycle 3), optional week 9 (Cycle 4) | ICE to begin at week 3/Cycle 2 |

Nivolumab only and NIVO + ICE dosing can be given during a window of ± 3 day due to scheduling issues.

Criteria for dose de-escalation in the 6-patient safety monitoring cohort for patients treated with nivolumab plus ICE (cycle 1): If $\leq 1/6$ patients experience unacceptable toxicity, then the study will continue. If 2 or more patients experience unacceptable toxicity, we will stagger the dose of nivolumab and ICE by 1 week so that nivolumab will start on day 1 and ICE will start on day 8 of a 21 day cycle. There will then be another 6 patient cohort added to the monitoring. If $\leq 1/6$ patients experience unacceptable toxicity in the staggered cohort, then the study will continue. If, however, 2 or more patients experience unacceptable toxicity in the staggered cohort, then nivolumab will not be given in combination with ICE.

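### Participating investigators may be told of an unexpected fatal or serious reaction as late as day 30, against day 7 or 15 for the FDA, and 30 days is longer than one NIVO + ICE cycle

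*Combined protocol and SAP*

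**What the plan says.** Three recipients of safety information have stated time limits.

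- **FDA (Section 14.2.4.1).** An unexpected fatal or life-threatening experience associated with the drug "must be reported to the FDA no later than 7 calendar days after initial receipt of the information". One that is serious and unexpected "must be submitted no later than 15 calendar days after initial receipt of the information". Section 14.2.4.2 repeats both limits.
- **Industry partner (Section 14.2.4.2).** "BMS will be provided with a simultaneous copy of all adverse events filed with the FDA".
- **Participating investigators (Section 14.2.4.3).** The Study PI or designee reports all reportable serious adverse events "as an IND Safety Report occurring within 30 calendar days of receipt of sponsor (lead site) notification". This one limit covers every such event, deaths included. IND safety reports that come from the industry partner are also forwarded to the sites, "indicating whether a consent form or protocol change is required within 30 days of notification to Study PI".

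In the other direction, Section 14.2.2 requires non-lead sites to report qualifying serious adverse events to the Data Coordinating Center and Study PI within 24 hours.

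On the dosing interval, Section 5.1.5 states: "Cycle length is 21 days for NIVO + ICE and 14 days for Nivolumab only". It allows 3 days either side of each dose. Sections 5.4.1 and 5.4.2 cap NIVO + ICE at 2 cycles in Cohort A and 3 in Cohort B.

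**The concern.** The people who decide whether to give, delay or stop the next cycle are the treating investigators, and theirs is the slowest of the stated limits. A site that first hears on day 29 of an unexpected death elsewhere in the trial has been informed in line with the protocol. If the limit is longer than the dosing interval, the protocol allows a further cycle to be given without information that the sponsor has already had to file with the FDA. What is at stake is patient safety and the consent of patients on treatment. The trial's error rates and power are not affected.

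**Working it through.** The plan gives no figure to reproduce here. The check compares its stated deadlines with its stated cycle length.

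**Inputs.** FDA limits of 7 and 15 days (14.2.4.1); site limit of 30 days (14.2.4.3); NIVO + ICE cycle of 21 days with a 3-day window (5.1.5); permitted NIVO + ICE delay of up to 14 days (7.2).

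**Step 1: difference between deadlines.** Assume both clocks start on the same day.

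- Unexpected fatal or life-threatening: 30 − 7 = 23 days.
- Other serious and unexpected: 30 − 15 = 15 days.

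**Step 2: does the 30-day window hold a cycle start?** The number of starts certain to fall in a window is the whole-number part of window ÷ interval, while cycles remain due.

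| Interval between cycles | 30-day site window | 23-day difference | 15-day difference |
|---|---|---|---|
| 18 days | at least 1 | at least 1 | none certain (15/18 = 83%) |
| 21 days | at least 1 | at least 1 | none certain (15/21 = 71%) |
| 24 days | at least 1 | none certain (23/24 = 96%) | none certain (15/24 = 63%) |

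The percentages are the chance of one start if the day of notice is equally likely to fall anywhere in the cycle. If one dose is 3 days early and the next 3 days late, the interval is 21 + 3 + 3 = 27 days, still under 30. A full 14-day delay gives 21 + 14 = 35 days, which can carry the next cycle past day 30. The result therefore applies to undelayed cycles.

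**Step 3: Cohort B schedule.** Counting from C1D1 as day 0, NIVO + ICE starts on day 14 (C2), day 35 (C3) and optionally day 56 (C4). Let notice reach the lead site on any day from day 0 to the day before the last NIVO + ICE start, and count the starts in the following 30 days.

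- Two combination cycles: at least one start on 35 of 35 days, two starts on 9 of 35.
- Three combination cycles: at least one start on 56 of 56 days, two starts on 18 of 56.

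This follows because the longest wait for the next combination start is 21 days.

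**Step 4: effect of shorter limits.** For a patient with a 21-day cycle still due and uniform cycle phase, the chance of starting it before notice is:

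- 30-day limit: 100%, since 30 > 21.
- 15-day limit: 15/21 = 71% (63% to 83% for intervals of 24 to 18 days).
- 7-day limit: 7/21 = 33% (7/24 = 29% to 7/18 = 39%).

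**The case against.** Several points on the other side are fair.

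- **Thirty days is an outer limit, and there are other channels.** Site investigators sit on the Protocol Management Team (Section 16.3), which monitors safety and applies the stopping rules. Institutional policies and the operations manual, which are not in the documents, may call for faster notice. This limits what can be said about practice. It does not supply a deadline: the team is only recommended to meet, with no interval given, and the rule in Section 12.3 acts on an overall toxicity rate of 33% or more and halts accrual. It does not time the notice of a single event or address patients already on treatment.
- **The two sections do not cover identical events.** The cover letter in 14.2.4.3 states whether the FDA was informed, so some site reports appear to concern events not filed with the FDA. The site report must also say whether the protocol or consent form needs to change, which takes time. Both points stand. They support keeping 30 days for those purposes, but not for unexpected deaths.
- **The clocks start differently.** The FDA clock runs from initial receipt of the information, the site clock from receipt of sponsor notification. The 23 and 15 days therefore need the common-start assumption.
- **Partner-issued reports.** The protocol shows no FDA filing clock for these, so no 23- or 15-day difference is shown. The 30 days in that sentence could also attach to the consent or protocol decision rather than to the forwarding.

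A reader might go further and infer that every patient on treatment at the other sites receives another dose between the FDA's deadline and the sites'. The documents do not support this. The 15-day difference is shorter than a 21-day cycle, and patients who have had their last cycle start none. A reader might also lean on the statement in Section 12.1.1 that the combination was untested. That statement justifies Cohort A's six-patient safety segment; the same section later reports 13 Cohort B patients treated with no signal of excess toxicity so far.

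**Conclusion.** The point holds as a mismatch between stated reporting limits. Section 14.2.4.3 sets a single 30-day limit for telling participating investigators, without a shorter tier for unexpected fatal or life-threatening events, while the FDA limit is 7 or 15 days and the industry partner is copied at once. With a common start, the sites' deadline is 23 or 15 days after the FDA's. The 30-day window is longer than a 21-day NIVO + ICE cycle, so a patient with an undelayed cycle still due can start it before the site must be told.

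This rests on the protocol's own time limits and on reading the site clock as starting when the lead site is notified. It does not show that any site was in fact informed late, or that a faster operational route is absent. No regulatory text from outside the documents is used. The change is worth making because the timing matters to treating investigators and the correction is cheap.

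**What to change.** In Section 14.2.4.3:

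1. For events that meet the criteria in 14.2.4.1, send the IND safety report to all participating investigators at the same time as the FDA filing, and no later than 7 or 15 calendar days after initial receipt of the information, whichever applies.
2. Keep 30 calendar days for reportable serious adverse events outside those criteria, so that they are not left without a site deadline, and for the decision on protocol or consent changes, which can follow the report.
3. Forward the industry partner's IND safety reports promptly on receipt, for example within the same 7 or 15 days, and state that the 30 days applies only to the consent or protocol decision.

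The cost is small. For FDA-reportable events the report already exists by day 7 or 15. The downside is a second short communication when the consent or protocol decision is made. As the figures above show, the change shortens the exposure without removing it. It alters reporting times only and no dosing or treatment rule.

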16.1 All Investigator Responsibilities

An investigator is responsible for ensuring that an investigation is conducted according to the signed investigator statement, the investigational plan, and applicable regulations; for protecting the rights, safety, and welfare of subjects under the investigator's care; and for the control of drugs under investigation.

16.2 Study Principal Investigator Responsibilities

The Study Principal Investigator is responsible for the conduct of the clinical trial, including overseeing that sponsor responsibilities are executed in accordance with federal regulations.

16.3 Protocol Management Team (PMT)

The Protocol Management Team (PMT) minimally consisting of the study principal investigator, collaborating investigators, site investigators, research nurse, clinical research associate/coordinator, and the study biostatistician is responsible for ongoing monitoring of the data and safety of this study, including implementation of the stopping rules for safety/toxicity.

The PMT is recommended to meet (in person or via teleconference) to review study status. The meeting is a forum to discuss study-related issues including accrual, SAE/AE/UPs experienced, study response, deviations/violations and study management issues. The appropriateness of further subject enrollment and the specific intervention for subsequent subject enrollment are addressed.

16.4 Quality Assurance

Clinical site monitoring is conducted to ensure that the rights of human subjects are protected, that the study is implemented in accordance with the protocol and regulatory requirements, and that the quality and integrity of study data and data collection methods are maintained. Monitoring for this study will be performed by the City of Hope Office of Clinical Trials and Monitoring (OCTM), within City of Hope's Office for Safety and Data Quality.

Details of clinical site monitoring are documented in the OCTM SOP and the Risk Based Monitoring (RBM) plan. These documents specify the frequency of monitoring, monitoring procedures, the amount of subject data to be reviewed, and the distribution of monitoring reports to the study team and the COH DSMC.

16.5 Risk Determination

This is a High Risk study as defined in the [City of Hope Institutional DSMP](#). This determination was made because the study involves a COH IND.

16.6 City of Hope Data and Safety Monitoring Committee

The COH Data and Safety Monitoring Committee (DSMC) will review and monitor study progress, compliance, toxicity, safety, and accrual data from this trial via the PMT Progress Report (submitted by the Study Principal Investigator according to the frequency outlined in the [City of Hope Institutional DSMP](#)). The DSMC is composed of clinical specialists with experience in oncology and who have no direct relationship with the study. Information that raises any questions about participant safety will be addressed with the Protocol Management Team.

17 Ethical and Regulatory Considerations

17.1 Ethical Standards

This study will be conducted in conformance with the principles set forth in *The Belmont Report: Ethical Principles and Guidelines for the Protection of Human Subjects of Research* (US National Commission for

the Protection of Human Subjects of Biomedical and Behavioral Research, April 18, 1979) and the Declaration of Helsinki.

17.2 Regulatory Compliance

This study is to be conducted in compliance with the IRB approved protocol and according to the following considerations:

US Code of Federal Regulations (CFR) governing clinical study conduct

Title 21 Part 11 – Electronic Records; Electronic Signatures

Title 21 Part 50 – Protection of Human Subjects

Title 21 Part 54 – Financial Disclosure by Clinical Investigators

Title 21 Part 56 – Institutional Review Boards

Title 21 Part 58 – Good Laboratory Practice for Nonclinical Laboratory Studies

Title 21 Part 312 – Investigational New Drug Application

Title 45 Part 46 – Protection of Human Subjects

US Federal legislation, including but not limited to:

Health Insurance Portability and Accountability Act of 1996

Section 801 of the Food and Drug Administration Amendments Act

Applicable state and local laws. For research occurring in California, this includes but is not limited to State of California Health and Safety Code, Title 17.

Applicable institutional research policies and procedures.

17.3 Institutional Review Board

Each participating institution must provide for the review and approval of this protocol and the associated informed consent documents by an appropriate IRB holding a current US Federalwide Assurance issued by and registered with the Office for Human Research Protections (OHRP). Any documents that the IRB may need to fulfill its responsibilities (such as protocol, protocol amendments, Investigator's Brochure, consent forms, information concerning patient recruitment, payment or compensation procedures, or other pertinent information) will be submitted to the IRB. The IRB's written unconditional approval of the study protocol and the informed consent document will be in the possession of the Investigator, and, for sites external to COH, the possession of the coordinating center, before the study is initiated. The Investigator will obtain assurance of IRB/IEC compliance with regulations.

The IRB will be informed of revisions to other documents originally submitted for review; serious unexpected or unanticipated adverse experiences occurring during the study, and any additional adverse experiences in accordance with the standard operating procedures and policies of the IRB; new information that may affect adversely the safety of the patients of the conduct of the study; an annual update and/or request for re-approval; and when the study has been completed.

Any amendment to the protocol document and accompanying informed consent document/template, as developed and provided by the Study PI, will require review and approval by the IRB before the changes are implemented in the study. The protocol and consent will be reviewed and approved by the COH IRB before submission to a participating site IRB.

17.4 Informed Consent

For a multi-site study, each participating institution will be provided with a model informed consent form. Each institution may revise or add information to comply with local and/or institutional requirements, but may not remove procedural or risk content from the model consent form. Furthermore, prior to submission to the IRB (initial submission and amendments), the consent and accompanying HIPAA form, if separate to the consent, must be reviewed and approved by the Data Coordinating Center.

After the study has been fully explained, written informed consent will be obtained from either the patient or his/her guardian or legal representative before study participation. The method of obtaining and documenting the informed consent and the contents of the consent must comply with the ICH-GCP and all applicable regulatory requirements.

Before implementing any study procedure, informed consent shall be documented by the use of a written consent form approved by the IRB/IEC and signed and dated by the patient or the patient's legally authorized representative at the time of consent. A copy of the signed informed consent will be given to the patient or patient's legally authorized representative. The original signed consent must be maintained by the Site Investigator and available for inspection sponsor designated representatives, or regulatory authority at any time.

Informed consent is a process that is initiated prior to the individual agreeing to participate in the study and continues throughout study participation.

